9.1.5 Secondary Efficacy Analysis

A two-sided 0.05 alpha level will be used.

For comparison of biomechanical measurements between a preoperative plan and postoperative measurements within the Rejuvenate[®] Modular Hip System group, a t-test or Wilcoxon test will be used.

Independent group t-tests will compare HHS, SF-12 and LEAS at each time point between the Rejuvenate[®] Modular Hip System and Secur-Fit[™] HA monolithic femoral stem groups. In addition, a paired t-test will compare the results preoperatively with each postoperative evaluation within the Rejuvenate[®] Modular Hip System group.

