2.1.2 Secondary

The secondary objectives of this study will be to measure natural preoperative biomechanical measurements for creation of a preoperative plan, and compare to postoperative biomechanical measurements, within the Rejuvenate® Modular Hip System group. It is expected that the postoperative measurements at the 6-week interval will be similar to the preoperative plan.

Additionally, pain, function and health-related QOL between the Rejuvenate® Modular Hip System group and the Secur-Fit™ HA monolithic femoral hip stem group will be compared at postoperative time points. It is expected that the HHS, SF-12 and LEAS outcomes in the study group will be non-inferior to the historical control.

Lastly, radiographic stability and complications between those implanted with the Rejuvenate® Modular Hip System and the Secur-Fit™ HA monolithic femoral stem group will be reviewed. Published complication rates with similar devices as well as complications related to modularity will be reviewed, as applicable.

Clinical Outcomes:

Clinical outcomes will be evaluated via the total HHS, including pain, motion and function, preoperatively, and at the 6-week, 1, 2, 3, 4 and 5-year visits. Additional HHS data will be obtained at the 7-year and 10-year time points at investigational sites that choose to bring their subjects back in for these optional visits.

Patient Outcomes:

The SF-12 is a 12 item patient self-assessment evaluating health and general well being. The LEAS is a tool that has been developed and validated to evaluate the level of patient activity. These tools will be used to assess patient health-related QOL and will be collected preoperatively, at the 6-week, 1, 2, 3, 4 and 5-year visits. Additional patient outcomes data will be obtained at the 7-year and 10-year time points at investigational sites that choose to bring their subjects back in for these optional visits. A questionnaire

CONFIDENTIAL

for patient completion, intended to provide information on patient satisfaction, pain and whether or not there have been any revisions or removals of the study device since the last follow-up visit, is required at the 6, 7, 8, 9 and 10-year visits.

Radiographic Outcomes:

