5.2 *Randomization*

This study will enroll under a non-randomized study design.

6 Device Description

6.1 *Study Device*

The Rejuvenate® Modular Hip System has been cleared for marketing in the United States, and, therefore, this study is considered a post-market assessment. All cases in this study will receive the Rejuvenate® Modular Hip System, consisting of the Rejuvenate® Modular Stem and the

CONFIDENTIAL

Rejuvenate® Modular Neck. Additionally, only the following **Stryker compatible** ancillary devices may be used, according to this study protocol:

- Stryker Trident® or Titanium™ Primary acetabular shells, with or without screw fixation, as well as Stryker Restoration® ADM acetabular shells
- Stryker alumina ceramic inserts (for use with Trident® acetabular shells) or X3® inserts
- Stryker LFIT™ CoCr heads; delta ceramic heads; or alumina ceramic heads with adapter sleeve

Device Description:

The Rejuvenate® Modular Hip System consists of a modular stem and a modular neck. It is similar to other modular and monolithic hip systems currently distributed. It is intended for cementless, press-fit application and is designed for use with currently available Stryker femoral heads. A description of the Rejuvenate® Modular Hip System components and compatible femoral heads follows. Stryker acetabular components compatible with the chosen Stryker femoral heads must be used, according to this study protocol. Appendix C gives an overview of all protocol-specified components.

Modular Stem:

The modular stem design is based on the Secur-Fit™ system. The Rejuvenate® Modular Hip System includes a straight stem with a normalization pattern on the anterior and posterior aspects of the proximal end of the stem to facilitate press-fit stability and load transmission in the proximal region of the femur. The stem has an internal opening which mates with the modular neck via an oblong Morse-type taper. The drawing below depicts the stem design.

CONFIDENTIAL

The Rejuvenate® Modular Stem will be available in sizes 7, 8, 9, 10, 11 and 12. The Rejuvenate® Monolithic Stem will be available in sizes 4, 5 and 6; however, **the Rejuvenate® Monolithic Stem may not be used according to this protocol**. Patients requiring a femoral stem in size 4, 5 or 6 should not be enrolled into the study. Investigators should template the femoral stem size to be used prior to completing the Inclusion/Exclusion CRF for enrollment into the study.

[figure not shown]

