7.1 Preoperative Visit

During the preoperative visit, patients that are possible candidates for this study will be screened to determine if they meet the inclusion/exclusion criteria. If the patient is a candidate, the investigator will propose participation in the study to the patient, according to GCP guidelines. Patients must sign an IRB approved study consent form prior to participating in any study related activities. Consent must be obtained within four months of surgery.

Once the subject has been consented, preoperative data will be collected including: demographics, medical history, HHS, AP hip, AP pelvis and lateral radiographs, SF-12, and LEAS.

Additionally, the investigator will measure the following from preoperative radiographs, including:

- Leg length discrepancy (millimeters)
- Natural femoral offset (millimeters)
- Natural femoral neck angle (degrees)
- Qualitative assessment of natural femoral version (Retroverted, Neutral, Anteverted)

The investigator will then proceed with a preoperative plan from templating, reflecting desired postoperative measurements and the component sizes, angles, and offsets that will be used to achieve the following measurements:

Preoperative Distance from Planned Center of Rotation

- Vertical distance from the anatomic hip center to the planned center of rotation of the hip (millimeters)
- Horizontal distance from the anatomic hip center to the planned center of rotation of the hip (millimeters)

CONFIDENTIAL

Components to be Used

- Acetabular cup size
- Femoral neck angle [127°, 132°, 130° (The 130° neck angle is only available in 16° of version.)]
- Femoral neck length (millimeters)
- Femoral head size
- Femoral head offset
- Femoral stem size*
- Femoral version (0°, ±8°, ±16°)

*The Rejuvenate® Modular Stem will be available in sizes 7, 8, 9, 10, 11 and 12. The Rejuvenate® Monolithic Stem will be available in sizes 4, 5 and 6; however, **the Rejuvenate® Monolithic Stem may not be used according to this protocol**. Patients requiring a femoral stem in size 4, 5 or 6 should not be enrolled into the study. Investigators should template the femoral stem size to be used prior to completing the Inclusion/Exclusion CRF for enrollment into the study.

Additional Planned Measurements

- Amount of leg length to be restored (millimeters)
- Femoral offset to be achieved (millimeters)
- Qualitative assessment of planned postoperative femoral version (Retroverted, Neutral, Anteverted)

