9.1.2 Secondary Efficacy Parameters

The secondary efficacy parameters include:

- Biomechanical measurement change from preoperative plan at 6-week visit
- HHS at each visit
- SF-12 scores at each visit
- LEAS at each visit

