9.2.2 Safety Analysis

All AEs will be listed, tabulated and summarized by event, number and percent of cases/subjects. AE rates and 95% confidence intervals will be presented. In addition, a

CONFIDENTIAL

Fisher's exact test will be used to compare the AE rates between the Rejuvenate® Modular Hip System and the Secur-Fit™ HA groups or cohorts, if appropriate.

For categorical variables, such as radiographic stability, the number and percent in each category will be presented.

9.3 *Missing Data*

No missing data will be imputed for the primary analysis and secondary analyses.

9.4 *Statistical Methodology*

9.4.1 *Data Summary*

The following is a detailed proposal of statistical analyses planned for data collected during the study.

Descriptive statistics will be computed for all preoperative conditions and demographic parameters. That is, for continuous data (e.g. HHS) the N, mean, median, standard deviation, minimum and maximum will be computed. For categorical data (e.g. gender) the frequency will be computed. If appropriate, the data will be presented by the Rejuvenate® Modular Hip System and the Secur-Fit™ HA groups.

Descriptive statistics and statistical comparisons for important demographic, efficacy and safety variables will be provided in tables.

A survival analysis for revision/removal of the modular femoral stem/neck construct will be performed.

9.4.2 *Sample Size Calculation*

Given an estimated revision rate for both groups at 2.5% and a non-inferiority margin of 5%, with a one-sided alpha of 0.05 and 80% power, a total of 147 cases per group are required to reject the null hypothesis that the revision rate for Rejuvenate® Modular Hip System cases is 5% greater than for Secur-Fit™ HA monolithic femoral stem cases. In order to control for a 20% drop-out rate, 183 cases per group are required.

CONFIDENTIAL

A total of 240 cases received the Secur-Fit™ HA femoral stem in the Trident® X3® Polyethylene Insert Study, a historical control. Therefore, although only 183 cases are needed for statistical power, 240 cases will be enrolled in the Rejuvenate® Modular Hip System Outcomes Study.

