please use "-")OPERATIVE SIDE: (Use one form per side)
 Right LeftVISIT DATE: / /
D D M M M Y Y Y Y

I. DEMOGRAPHICS

A. DATE OF BIRTH:

 / /
D D M M Y Y Y Y

F. GENDER: (Check One)

 Male Female

B. HEIGHT:

 inches

C. WEIGHT:

 lbs.

G. ETHNICITY: (Check One)

 Hispanic or Latino origin
 Not Hispanic or Latino origin

D. EDUCATION LEVEL: (Check One)

 < High School High School Diploma > High School

H. RACE: (Check all that apply)

 American Indian or Alaskan native
 Asian
 Black or African heritage
 Native Hawaiian or other Pacific Islander
 White

E. EMPLOYMENT STATUS: (Check One)

 Working Not Working

II. CIGARETTE AND ALCOHOL USE

I. CIGARETTE USE: (Check One)

 Non-smoker Current cigarette smoker# PACKS/DAY: . # YEARS: .

J. ALCOHOL USE: (Check One)

 Have never had alcohol Have not had alcohol in the last year < 3 drinks a week 3 - 7 drinks a week 8 - 14 drinks a week 15+ drinks a week Ex-cigarette smoker# PACKS/DAY: . # YEARS: . Date Stopped
 / /
D D M M M Y Y Y Y

III. DIAGNOSIS

K. INITIAL DIAGNOSIS: (Check One)

 Osteoarthritis Traumatic Arthritis Avascular Necrosis Other (Specify) _____

SUBJECT ID:

6 8

Site #

Subject #

GENERAL INFORMATION

SUBJECT INITIALS:

(If there is no middle initial please use "-")

--	--	--

OPERATIVE SIDE:

(Use one form per side)

 Right Left

IV. PRESENT MEDICAL STATUS

L. CONCURRENT MEDICAL CONDITION: (Specify)

 None Cancer Cardiovascular Dermatologic Digestive Endocrine / Metabolic Immunologic / Lymphatic Musculoskeletal Neurologic Psychologic Respiratory Substance Dependence Urogenital Other (Specify)

V. COMMENTS

INVESTIGATOR NAME (PRINT):

INVESTIGATOR SIGNATURE:

DATE:

--	--

 /

--	--	--

 /

--	--	--

 D D M M M Y Y Y Y

INITIAL/DATE:

Receipt _____

Stamp Date Received:

Entry _____

For Stryker Use Only

Verification _____

Monitored _____

[name]

SUBJECT ID: **6 8**
Study # Site # Subject #

GENERAL INFORMATION

SUBJECT INITIALS:
(If there is no middle initial
please use "-")

OPERATIVE SIDE: (use one form per side)

 Right LeftVISIT DATE: / /
D D M M M Y Y Y Y

I. PAIN

A. PAIN (Check One)

- None, or ignores it
- Moderate pain, tolerable but makes concessions to pain. Some limitations of ordinary activity or work. May require occasional pain medication stronger than aspirin
- Slight, occasional, no compromise in activities
- Marked pain, serious limitation of activities

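### HHS, SF-12 and LEAS are compared with a non-randomised historical control by unadjusted t-tests, so measured case-mix differences could be read as device effects or hide one

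*Combined protocol and SAP*

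**What the plan says.** Section 5.2 states: "This study will enroll under a non-randomized study design". The comparator is the 240 Secur-Fit HA cases from the Trident X3 "Polyethylene Insert Study, a historical control" (section 9.4.2).

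For the three scores, section 9.1.5 sets a two-sided 0.05 level and says "Independent group t-tests will compare HHS, SF-12 and LEAS at each time point between the" two device groups. It names no covariate. The synopsis repeats the t-tests, but at whichever time points are applicable. Section 9.1.2 lists "HHS at each visit" and does the same for SF-12 and LEAS. Section 2.1.2 says that the scores in the study group and the "monolithic femoral hip stem group will be compared at postoperative time points", and it expects non-inferiority. No margin for these scores appears anywhere.

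Baseline data are collected in the study arm. Section 7.1 says "Once the subject has been consented, preoperative data will be collected including: demographics, medical history, HHS", and continues with radiographs, SF-12 and LEAS. The Demographics form in Appendix F records date of birth, gender, height and weight, and has the item "K. INITIAL DIAGNOSIS: (Check One)".

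The planned use of these data is descriptive. Section 9.4.1 says "Descriptive statistics and statistical comparisons for important demographic, efficacy and safety variables will be provided in tables", with presentation by group where appropriate. The only test that uses a preoperative score as reference is the paired t-test in 9.1.5, which stays within the Rejuvenate group.

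**The concern.** Without randomisation, patients in the two studies may differ in preoperative score, age, sex, BMI or diagnosis. If such a factor predicts the follow-up score, an unadjusted difference in means mixes it with the device effect. The result can favour either device.

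The study arm has entry features that could shift its case mix. It takes only femurs that template to stem sizes 7 to 12 (section 4.1), and each center starts enrolling only after three cases with the system (section 3.4). The documents do not say whether the control cohort had similar restrictions. This makes an imbalance plausible but does not show one.

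The comparison carries weight because section 2.1.2 expects these scores to be non-inferior to the control. Bias in favour of the new device would make that expectation look met too easily. Bias the other way could hide that it was met.

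A smaller, separate matter is that the t-tests treat hips as independent. Appendix A and Appendix G both foresee subjects with two enrolled hips.

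**Working it through.** **Figure to reproduce.** There is none. The documents give no sample size, SD, effect size or power for HHS, SF-12 or LEAS. The 147 and 183 cases per group in section 9.4.2 belong to the primary endpoint.

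**Is there adjustment anywhere?** Sections 9.1.5, 9.3, 9.4.1 and 9.4.4 and the synopsis contain no covariate model, between-group comparison of change, matching, stratification or propensity method. A preoperative between-group test might be implied by 9.1.2 and 9.1.5, but 2.1.2 restricts the comparison to postoperative times. Such a test would show an imbalance without removing it.

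**Illustration of size.**

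Inputs from the documents:
- 240 cases per group and 20% drop-out (9.4.2), so 240 × 0.8 = 192. Applying the drop-out to the control is an assumption.
- Two-sided alpha of 0.05 (9.1.5).

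Inputs that are assumptions:
- A preoperative HHS difference D = 5 points.
- A slope of follow-up on preoperative score of 0.3.
- An SD of 10, 15 or 20 points.
- No true device effect.

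Formulas:
- Bias = slope × D = 0.3 × 5 = 1.5 points.
- SE = SD × √(2/192) = 0.102 × SD.
- False-positive rate = Φ(−1.96 + bias/SE) + Φ(−1.96 − bias/SE).

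| SD | SE | bias/SE | Rate, 192 per group | 147 per group | 240 per group |
|---|---|---|---|---|---|
| 10 | 1.02 | 1.47 | 0.312 | 0.251 | 0.376 |
| 15 | 1.53 | 0.98 | 0.165 | 0.138 | 0.195 |
| 20 | 2.04 | 0.73 | 0.114 | 0.099 | 0.130 |

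The result depends heavily on the inputs. With the imbalance in SD units and correlation in place of slope, 192 per group gives 6.0% for 0.1 SD and correlation 0.3. It gives 68.8% for 0.5 SD and correlation 0.5.

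**Effect of ANCOVA.** In simulation under the first set of inputs (192 per group, 6,000 runs), the t-test rejected in 31.6% (SD 10) and 10.9% (SD 20) of runs. ANCOVA on the preoperative score rejected in 4.8% and 4.6%. This recovery is built into the set-up, where that one score carries all the bias.

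Precision hardly changes. With equal SDs, so that correlation r = slope = 0.3, the variance factor is (1 − r²) × (1 + D²/(4·SD²)):
- D = 5, SD 10: 0.91 × 1.0625 = 0.967.
- D = 5, SD 20: 0.91 × 1.0156 = 0.924.
- D = 10, SD 10: 0.91 × 1.25 = 1.14, a loss of precision.

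**Clustering.** The footnote to Table 4 (section 12.3) gives 2,966 hips in 2,697 subjects over seven pooled sponsor studies. With at most two hips each, 2,966 − 2,697 = 269 subjects were bilateral, contributing 538/2,966 = 18.1% of hips. If both groups here were similar, the design effect is 1 + 0.181 × ICC, that is 1.09 at ICC 0.5 and 1.18 at ICC 1. The actual level, 2 × (1 − Φ(1.96/√design effect)), is then 6.1% to 7.1%.

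**The case against.** The strongest reply has four parts.

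- **The plan lets readers see an imbalance.** Section 9.4.1 promises tables and statistical comparisons of important demographic variables. This is true, but a table does not correct the postoperative difference, and an adjustment chosen after seeing it would be post hoc.
- **The remedy may not be available.** The documents do not describe the control study's baseline variables. If preoperative scores were not recorded there, only demographic adjustment is possible and the recovery shown above does not apply. This stands, and the fix has to be conditional on it.
- **ANCOVA is one choice among several.** Change-score and propensity methods rest on other assumptions and can give different answers without randomisation. This also stands. What matters is that one method is fixed in advance.
- **A two-sided false-positive rate is not the error that matters for a non-inferiority expectation.** That error depends on the direction of the bias and on a margin, and the documents give neither. This stands as a limit on the illustration.

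A reader might go further and infer that the two groups are known to differ, or that this trial has a false-positive rate of up to 31%. The documents support neither. They report no baseline data for either group, and the percentages follow from an assumed imbalance, slope and SD. The 31% case needs a 5-point gap at SD 10, which is half an SD. Nor would adjustment make the comparison equivalent to a randomised one: study, centre and era coincide completely with group.

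**Conclusion.** The concern holds in limited form. The plan compares three secondary scores with a non-randomised historical control without adjustment, although the study arm already collects the obvious covariates. Measured case-mix differences could create or mask an apparent device effect.

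The size and direction for this trial cannot be derived. The illustrated 11% to 31% at 192 per group rests wholly on assumed inputs, and smaller imbalances would matter little. The reason to adjust is to reduce bias, not to gain precision. Treating hips as independent is a minor addition, taking 5% to about 6–7% if the pooled bilateral rate applied.

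These are secondary endpoints with no stated success rule, so the plan should be changed on this point, but the primary conclusion does not depend on it.

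**What to change.** Replace the postoperative between-group t-tests in **both** section 9.1.5 and the synopsis, so that the two agree, with:

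> At each required postoperative visit through 5 years, HHS, SF-12 and LEAS will be compared between groups by ANCOVA with group as the factor and the preoperative value of the same score, age, sex, BMI and initial diagnosis as covariates, with standard errors clustered by subject. The adjusted mean difference and 95% CI will be reported. Unadjusted differences and preoperative values will be tabulated by group. Data from the optional 7- and 10-year visits will be summarised descriptively.

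The optional visits are left out of the comparison because only sites that choose to hold them contribute data.

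Also:
- Before analysis, and without sight of outcomes, confirm which covariates the control database holds. Adjust for those available and name those missing. If the preoperative score is missing for the control, state that bias from it remains.
- State that adjustment cannot remove study, centre or era differences.
- State that a non-inferiority conclusion on these scores would need a prespecified margin, which the documents do not give.
- Leave the primary 5-year confidence interval analysis unchanged. At the planned 2.5% revision rate, about 192 × 0.025 = 4.8 revisions per group are expected, too few for a covariate model to replace it.

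**Cost.** SAP wording, modest programming and access to patient-level control data. Cases without a preoperative score drop out of that score's comparison, consistent with no imputation (9.3) and the per protocol rule (9.4.4). The result relies on the ANCOVA model, measurement error in the preoperative score leaves some bias, and the interval may be wider if the imbalance is large.

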Statistical Methodology	
Primary:
 
The 90% confidence interval around the difference in success rate (Rejuvenate® Modular Hip System – Secur-Fit™ HA monolithic femoral stem) will be computed at 5 years postoperative. For the non-inferiority comparison, the lower bound of this 90% confidence interval will be compared with -5%.
 
Secondary:
 
• A t-test or Wilcoxon test will be used to compare the postoperative biomechanical measurements to a preoperative plan.• Independent group t-tests will also compare HHS, SF-12 and LEAS at applicable time points between the Rejuvenate® Modular Hip System and Secur-Fit™ HA monolithic femoral stem groups. In addition, a paired t-test will compare the results preoperatively with each postoperative evaluation within the Rejuvenate® Modular Hip System group.• The adverse event (AE) rates and 95% confidence intervals will be presented within the Rejuvenate® Modular Hip System group. A Fisher's exact test will be used to compare the AE rates between the Rejuvenate® Modular Hip System and the Secur-Fit™ HA groups, if appropriate.• Radiographic data will be summarized in table format.
--------------------------------	---

CONFIDENTIAL

Evaluation Schedule

Evaluation	Preop X-rays (-1 yr) CRFs (-4 mos)	Intraop	6 weeks (± 3 wks)	1 year (± 2 mos)	2 years (± 2 mos)	3 years (± 3 mos)	4 years (± 4 mos)	5 years (± 4 mos)	6 years (± 4 mos)	7 years (± 4 mos)	8 years (± 4 mos)	9 years (± 4 mos)	10 years (± 4 mos)
Inclusion/ Exclusion	X												
Demographics & Medical History	X												
Preoperative Functional Evaluation	X												
Preoperative Biomechanical Measurements	X												
Surgical Details		X											
Postoperative Functional Evaluation			X	X	X	X	X	X		Optional			Optional
Postoperative Biomechanical Measurements			X										
SF-12	X		X	X	X	X	X	X		Optional			Optional
LEAS	X		X	X	X	X	X	X		Optional			Optional
Radiographs: Anteroposterior (AP) pelvis, AP femur, lateral	X		X	X	X	X	X	X		Optional			Optional
Follow-up Questionnaire									X	X	X	X	X

Functional Evaluation: The Functional Evaluations include the HHS, a subjective outcomes tool completed by the investigator that measures function, pain and motion.

SF-12: The SF-12 is a 12 item patient questionnaire that evaluates general health and well being.

LEAS: The LEAS is a self-administered patient evaluation designed to reflect patient activity.

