3.2 Number of Centers

Cases will be enrolled at 10 to 12 centers in the United States. The enrollment goal ranges from 20 to 24 THA cases per center, utilizing the Rejuvenate® Modular Hip System. The enrollment goal range is dependent upon the number of participating centers. Although a range is presented, there is no maximum limit to the number of cases that a center may enroll. In the event that a center far exceeds the enrollment goal, Stryker may ask the center to cease enrollment so as not to skew the data. All participating centers will comply with the federal regulations regarding patient informed consent and IRB approval. Non-compliance of a study center may result in termination of the center's participation in the study.

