3.3 Number of Subjects

A total of 240 cases will be enrolled in this study. All cases will receive the Rejuvenate® Modular Hip System. Additionally, only the following ancillary devices may be used according to this study protocol:

- Stryker Trident® or Tritanium™ Primary acetabular shells, with or without screw fixation, as well as Stryker Restoration® ADM acetabular shells
- Stryker alumina ceramic inserts (for use with Trident® acetabular shells) or X3® inserts
- Stryker LFIT™ CoCr heads; delta ceramic heads; or alumina ceramic heads with adapter sleeve

The Rejuvenate® Modular Hip System is described in detail in Section 6 of this protocol, Device Description.

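### The between-group t-tests of HHS, SF-12 and LEAS ignore centre, so their nominal 5% error will be exceeded if outcomes correlate within centres and the two groups come largely from different centres

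*Combined protocol and SAP*

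**What the plan says.** Section 9.1.5 sets the between-group analysis of the secondary outcomes: "Independent group t-tests will compare HHS, SF-12 and LEAS at each time point between the" Rejuvenate and Secur-Fit HA groups. The error level is given in the same section: "A two-sided 0.05 alpha level will be used". Nothing in section 9 names a centre or investigator term, a mixed model, a clustered variance or an ICC.

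On the source of the study group, section 3.2 states: "Cases will be enrolled at 10 to 12 centers in the United States", and "The enrollment goal ranges from 20 to 24 THA cases per center, utilizing the Rejuvenate® Modular Hip System". It adds that "there is no maximum limit to the number of cases that a center may enroll", but also that the sponsor may ask a centre far above the goal to stop enrolling. Section 3.3 states: "A total of 240 cases will be enrolled in this study". Under section 5.1 every enrolled subject receives the Rejuvenate system.

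On the control group, section 9.4.2 states: "A total of 240 cases received the Secur-Fit™ HA femoral stem in the Trident® X3® Polyethylene Insert Study, a historical control". The number, size and identity of the control centres are not given.

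The notes to the Evaluation Schedule describe the HHS as "a subjective outcomes tool completed by the investigator that measures function, pain and motion". The same notes describe the SF-12 as a patient questionnaire and the LEAS as self-administered.

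**The concern.** An independent-group t-test takes its standard error from case-to-case variation alone. Within this study, centre is nested entirely in one group. If the control cases come from other centres, variation between centres (surgeon, case mix, rehabilitation) does not cancel in the group difference. It adds to the variance of that difference, and the t-test leaves it out. P-values and confidence intervals would then be too optimistic in either direction, and chance differences between centres could be read as a device effect.

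For the HHS there is a further source of within-centre correlation, because the investigator scores it. That argument does not carry to the SF-12 and LEAS, which patients complete, although other centre effects may remain there.

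The protocol itself treats centre as relevant. Section 3.2 lets the sponsor halt a centre far above its goal so that it does not distort the data, and section 3.4 requires three cases at a centre before enrolment to allow for a learning curve. The analysis then makes no use of centre. The issue would remain with one hip per person, so it is separate from any dependence between two hips of one subject.

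**Working it through.** **Inputs from the documents.** 240 cases per group (sections 3.3 and 9.4.2); 10 to 12 Rejuvenate centres (3.2); two-sided 0.05 (9.1.5); 20% drop-out (9.4.2). The plan's cluster size reproduces: 240/12 = 20 and 240/10 = 24. The plan gives no sample size or power for the secondary comparisons, so there is no such figure to reproduce.

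**Assumptions.** The documents give no ICC; 0 to 0.10 is shown. The control cluster size is unknown; two cases are shown, control clustered like the study group and control not clustered. The main calculation takes the two groups' centres to be different.

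**Formulas.** With m cases per centre, the design effect is DE = 1 + (m − 1) × ICC. The true variance of the group difference, relative to what the t-test assumes, is V = DE if both groups are clustered alike and V = (1 + DE)/2 if only one is. The actual two-sided error is 2 × (1 − Φ(1.96/√V)).

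**One line in full (m = 24, ICC 0.05).** DE = 1 + 23 × 0.05 = 2.15. Both groups clustered: √2.15 = 1.47, 1.96/1.47 = 1.34 and the error is 18.1%. Only Rejuvenate clustered: V = (1 + 2.15)/2 = 1.575, √V = 1.255 and the error is 11.8%. Effective cases per clustered group: 240/2.15 = 112.

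**Results for m = 20 to 24.**

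| ICC | DE | Standard error too small by factor (both clustered) | Effective N per clustered group | Error, both clustered | Error, only Rejuvenate clustered |
|---|---|---|---|---|---|
| 0 | 1.00 | 1.00 | 240 | 5.0% | 5.0% |
| 0.01 | 1.19-1.23 | 1.09-1.11 | 195-202 | 7.2-7.7% | 6.1-6.3% |
| 0.02 | 1.38-1.46 | 1.17-1.21 | 164-174 | 9.5-10.5% | 7.2-7.7% |
| 0.05 | 1.95-2.15 | 1.40-1.47 | 112-123 | 16.0-18.1% | 10.7-11.8% |
| 0.10 | 2.90-3.30 | 1.70-1.82 | 73-83 | 25.0-28.1% | 16.0-18.1% |

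**After 20% drop-out.** 240 × 0.8 = 192 cases, so 192/12 = 16 to 192/10 = 19.2 per centre. With both groups clustered, the error is 6.8-7.1%, 8.6-9.3%, 13.8-15.6% and 21.5-24.3% at ICC 0.01, 0.02, 0.05 and 0.10.

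**Simulation check** (40,000 runs per setting, 10 × 24 and 12 × 20 cases per group, different centres). The t-test error was 7.4-7.6%, 9.6-10.6%, 16.1-18.0% and 24.7-27.7% at the same four ICCs, in agreement with the formula. An analysis of centre means, used as a simple stand-in for a random centre effect, gave 4.8-5.2%. The mixed model itself was not simulated.

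**Same centres in both groups** (10 × 24, equal numbers, stable centre effects). The plain t-test error was 4.1-5.0% over ICC 0 to 0.10, so there is no inflation.

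**The case against.** The strongest reply is that the excess error rests on two things the documents do not give: a positive ICC, and control centres that differ from the study centres. Both are from the same sponsor, so some overlap is possible, and with full and equal overlap the inflation disappears. This stands, and it makes the conclusion conditional. It does not rescue the plan, which gives no ground for assuming overlap and does not ask for it to be checked.

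Second, the goal of 20 to 24 belongs to the Rejuvenate study and cannot be taken as the control's cluster size; drop-out also shrinks the clusters. This stands too, and is why the one-group and drop-out figures are shown. On unequal centre sizes, the absence of a fixed cap is tempered by the sponsor's discretion to halt a centre far above its goal.

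Third, these are secondary outcomes. Section 2.1.2 expects non-inferiority on them, which a two-sided difference test without a margin does not test. That is a separate gap. A standard error that is too small would also make a non-inferiority interval too narrow.

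A reader might extend the point to the primary comparison in section 9.1.4. The documents do not support that. The section does not say how its 90% interval is calculated. At the assumed 2.5% revision rate about 6 revisions per group are expected (0.025 × 240), too few over 10 to 12 centres for a clustered interval to be dependable. At an assumed ICC of 0.01, 240 enrolled cases are worth 195-202, still above the 183 that section 9.4.2 asks for, so no consequence is shown.

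**Conclusion.** The point holds in conditional form and for section 9.1.5 only. The planned t-tests deliver their 5% error only if there is no within-centre correlation, or if the same centres supply both groups in a balanced way. The plan establishes neither.

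If outcomes correlate within centres and the groups come largely from different centres, the actual error runs from about 6-8% at ICC 0.01 to about 16-28% at ICC 0.10, depending on whether the controls are clustered as well, and somewhat less after drop-out. The ICC, the control cluster sizes and the degree of centre overlap are all assumptions.

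Two stronger readings go too far. One is that the 5% level is certainly exceeded; the documents do not give the facts needed to say so. The other is that investigator scoring affects all three outcomes; it applies to the HHS alone.

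**What to change.** In section 9.1.5, replace the between-group t-tests of HHS, SF-12 and LEAS with a linear mixed model having a fixed group effect, a random centre effect and Kenward-Roger degrees of freedom. State in the plan how many centres supplied the control cases, how many cases each supplied, and how far those centres overlap with the centres of this study. Leave section 9.1.4 as it is on this point.

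The model suits each possibility. With an ICC near zero it changes little; with shared centres it can use the contrast within centres; with different centres it carries the between-centre variance into the standard error. It does not remove systematic differences between this study and a historical control.

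The cost is SAP wording and a few lines of code, with no new visits or patients. The site number is already part of the subject ID on this study's CRFs (Appendix F). The documents do not show that the control data carry site identifiers, so this must be confirmed first. The downside is wider intervals.
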